### 3.1.3 Selection of sites and physicians

The intent of the registry is to actively pursue and capture as many as possible of the fingolimod maternally exposed pregnancies identified; therefore, there is no limit to the number or type of physicians and/or patients that may contribute data to the registry.

#### 3.2 Exposure of interest

The exposure of interest is fingolimod exposure during pregnancy or immediately prior to becoming pregnant (up to 8 weeks before LMP).

#### 3.3 Study endpoints

One outcome of interest is major malformations, which are defined as any structural defect with surgical, medical, or cosmetic importance recognized. In addition, data on minor

Page 15

congenital anomalies and overall pregnancy outcomes will be collected i.e., spontaneous fetal loss, stillbirth and induced abortion. Complications during pregnancy will also be recorded. Data on potential adverse effects on the physical and immune system development of the offspring, and any other adverse pregnancy and maternal outcomes will be collected. If the pregnancy outcome is a live birth involving a congenital anomaly or other outcome for which there is evidence of a congenital anomaly, patient data will be forwarded to the independent registry clinical reviewer (e.g. a teratologist) who will complete a congenital anomaly evaluation.

The following physical features will be collected but will not be recorded as major malformations:

- Minor anomalies, i.e., anomalies with no serious medical or cosmetic consequence to the child
- Positional deformities, i.e., a positional deformity that usually normalizes spontaneously after about 3 months of age, e.g., abnormal head shape, torticollis.
- Features of pre-maturity.
- Chromosome abnormalities.
- Genetic disorders.

#### 3.4 Data collection

All data will be collected on eCRFs (or on paper CRFs and centrally entered) and stored in the EDC system. The EDC system is designed with a customizable workflow which will present the visit specific forms to the user.

- For data capture, the eCRFs will correspond to six different time-based assessment periods: baseline, mid-second trimester, post-partum (up to 3 months after estimated date of delivery (EDD)), 3 month follow-up (from 3 months after EDD up to infant age 9 months), one year follow-up (10 to 14 months), and discontinuation (including early termination/end of study).
- Additionally, separate forms are used for the reporting of an adverse event, maternal
  conditions, prenatal testing, congenital malformation, healthcare provider log and
  concomitant medications.

If the patient's HCP is not able to provide the information needed, any information known by the mother will be solicited directly from her by the registry team (where allowed by local regulation) and recorded as medically unconfirmed by a HCP. For any safety outcomes all efforts will be made to obtain a confirmation by a HCP.

The data to be collected in each CRF are specified in Sections 3.4.1 to 3.4.6 and summarized in Table 3-1 for the patient/fetus and Table 3-2 for the infant.

Table 3-1 Recommended schedule of data collection: Maternal and fetal exposures and outcomes

Visit	Baseline	Mid-2 nd Trimester	Post- partum	End of Registry or Premature Discontinuation
Window	At enrollment	21 weeks gestational age +/- 2 weeks	Up to 3 months after EDD	At the end of patient's participation
Informed Consent	Х			
Maternal demographics	Χ			
MS disease and treatment history	Χ			
Gestational age at enrollment (by LMP or ultrasound)	X			
Obstetrical history, including previous pregnancy outcomes and sibling information	X			
Relevant maternal/paternal family history of pregnancy complications/congenital abnormalities	X			
Medical history/newly diagnosed conditions of mother	X			
Fingolimod dosing and administration	X	Χ	Χ	X
Prenatal test results	Χ	X	Χ	Χ
Other exposures, including lifestyle factors and concomitant medications	X	X	X	X
Participation in fingolimod studies*	Χ			
Obstetric and delivery complications			X	Χ
Pregnancy outcome, including gestational age at outcome			Χ	X
Major and minor malformations	Χ	X	X	Χ
Adverse events	Χ	X	X	Χ
Reason for premature discontinuation				X

\* Fingolimod clinical trials and any non-interventional fingolimod studies.

Table 3-2 Recommended schedule of data collection: Infant outcomes

Visit	Post-partum	3 months Follow-up	One Year Follow-up	Premature Discontinuation
Window	Up to 3 months after EDD	EDD + 3 months to infant age 9 months	Infant age 10 to 14 months	At the end of infant's participation
Informed consent for infant	X			_
Infant outcome details	X	X	Χ	X
Major and minor malformations**	X	X	Χ	X
Infant height, weight and head circumference	X		X	X
Infant medical conditions, including testing/procedures and diagnoses	X		X	X
Breastfeeding history and duration			Χ	X
Neurodevelopmental milestone status			X	X
Adverse events	X	X	Χ	Χ
Reason for early discontinuation				X

\*\* In addition to occurrence, detailed information on major and minor malformations (e.g., diagnostic or pathology results) are to be collected when available.

#### 3.4.1 Enrollment/baseline

Patients will be formally enrolled by a HCP or by the CRO (refer to Section 6.1 for further details regarding enrollment procedures). A patient is defined as being enrolled once she has signed the informed consent form.

Once a patient has provided their informed consent for participation in the registry, a non-patient identifying registry ID number will be assigned to each participant. To ensure confidentiality, no direct patient identifying information will be included in the registry database used for data collection of clinical information. Patient and HCP(s) contact details which were collected during the enrollment process will be kept separate and protected by the site for follow-up purposes only. Examples of patient contact information details include two forms of contact for the eligible patients as well as the contact information of two other persons who know the patient (e.g., a family member or a friend living outside of the patient's home).

Once enrolled, patients will be observed until the end of the planned participation or termination of the registry.

The following baseline information will be collected and reported to the registry:

- Documentation of informed consent.
- Date of contact
- Reporter type (e.g., patient, neurologist, obstetrician, midwife, other HCP).

- Multiple sclerosis disease history, including years since onset of MS symptoms, years since MS diagnosis, initial course (e.g., relapsing remitting, secondary progressive), previous exposure to disease-modifying therapies.
- Fingolimod exposure including dosing and dates of administration including start and end dates of dosing period during various trimesters of pregnancy.
- Demographic characteristics, including maternal age at last menstrual period (LMP) and ethnicity.
- LMP and EDD (preferably by earliest ultrasound).
- Maternal height and weight (for calculated body mass index (BMI)).
- Gestational age at enrollment (by LMP and/or ultrasound, if available).
- Targeted prenatal testing performed (yes/no).
- Date and results of any prenatal tests performed such as ultrasound, amniocentesis, serum markers, NT screen and CVS.
- Significant maternal medical conditions other than MS (e.g., diabetes, hypertension, cardiovascular disease, epilepsy or seizure disorder, depression, hepatitis, thyroid disease, concomitant autoimmune disease).
- Obstetrical history, e.g., earlier pregnancies and outcomes if not primagravida, including information about siblings.
- Relevant maternal/paternal family history of pregnancy complications/congenital abnormalities.
- Other exposures, such as recreational drugs, including alcohol use, cigarette smoking and illicit drugs, as well as dosage and dosing regimen of other medical products used, including prescription products, over-the-counter products, dietary supplements, vaccines, and insertable or implantable devices.
- Information on whether the patient is participating in any other fingolimod studies (including clinical trials and non-interventional studies).
- Contact information for the mother's HCP(s).

## 3.4.2 Mid-2nd trimester (21 weeks gestational age +/- 2 weeks)

For patients enrolled during the first trimester, the following data will be collected during the mid-second trimester. For patients enrolled after week 19, baseline data will be collected and mid-2nd trimester data collection is not needed.

- Date of contact/follow-up.
- Gestational age in weeks and days at time of follow-up by ultrasound or LMP.
- Information on any prenatal tests such as ultrasound, amniocentesis, serum markers, NT screen or CVS.
- Major or minor malformations identified.
- Pregnancy outcome (if not ongoing).
- If elective termination, specify primary reason (i.e., identified anomaly, increased risk of anomaly, non-medical reasons).
- Spontaneous abortion.

Page 19

Amended Protocol Version 03 clean

- Gestational age at pregnancy outcome (weeks).
- Updated fingolimod exposure and concomitant medication exposure information.

#### 3.4.3 Post-partum (up to 3 months after expected delivery date)

At the time of the estimated delivery the patient's registry site will be contacted by the registry team and asked to provide the necessary follow-up information. Although it is anticipated that data regarding pregnancy outcome will be provided by an obstetrician or other perinatal HCP, it may also be provided by the patient's neurologist, the patient herself or other physician if necessary. The patient's primary HCP may change during the course of follow-up and data may be collected from multiple sources. In order to prevent loss to follow-up and incomplete reports, alternative sources of information will be pursued as required, if contact information is available. As with all other time points, no direct patient identifiable information such as name and address will be reported to the registry. Baseline information and outcome as well as other follow-up assessment will be linked using the unique patient ID.

The following data will be collected post-partum:

- Documentation of informed consent for the infant.
- Date of contact, contact information (separate database) and specialty of HCP(s) providing information.
- Pregnancy outcome (term or preterm live birth, elective termination, fetal death).
- Date of pregnancy outcome or gestational age in weeks.
- If elective termination, specify primary reason (identified anomaly, increased risk of anomaly, non-medical reasons).
- Obstetric and delivery complications (preterm delivery, premature rupture of membranes (PROM), preeclampsia/severe pregnancy-induced hypertension (PIH)/proteinuria, gestational diabetes, intrauterine growth retardation (IUGR) and so on).
- Live births: whether single or multiple births (if multiple, number of fetuses).
- For each infant:
  - 1. Infant gender
  - 2. Birth length (in or cm)
  - 3. Gestational age (weeks, days)
  - 4. Birth weight (lbs/oz or grams)
  - 5. Head circumference (in or cm)
  - 6. Apgar scores (1, 5 and 10 minutes)
- Tests/procedures performed and any associated diagnoses.
- Infant vital status (alive / deceased).
- Presence of major congenital malformations, e.g., heart defect, spina bifida, club foot deformity, cleft palate.
- Presence of minor congenital malformations (i.e., anomalies with no serious medical or cosmetic consequence to the infant).
- Other conditions noted at or around birth (e.g., positional deformities, features of prematurity, chromosomal abnormalities, genetic disorders).

• Neonatal illnesses, need for resuscitation/hospitalization/neonatal intensive care and drug therapies administered.

#### 3.4.4 Three-month follow-up (infant age 3 to 9 months)

The following data will be collected at the three-month follow-up:

- Date of contact, contact information (separate database) and specialty of healthcare provider(s) providing information.
- For each infant:
  - 1. Infant vital status (alive / deceased)
  - 2. Any major or minor malformation(s) diagnosed since initial birth report
  - 3. Other conditions noted at or around birth (e.g., positional deformities, features of prematurity, chromosomal abnormalities, genetic disorders).

## 3.4.5 One-year follow-up (infant age 10 to 14 months)

The following data will be collected at one-year follow-up for each infant:

- Date of contact
- Any major or minor malformation(s) diagnosed since initial birth report.
- Infant vital status (alive / deceased).
- Infant height, weight and head circumference.
- History of significant diseases, including any requiring hospitalization and medications.
- Relevant testing/procedures performed and any associated diagnoses (if a specific diagnosis is not possible or available, the results/findings of the testing should be reported for completeness).
- Potential adverse effects on immune system development (e.g., serious infections requiring hospitalization).
- Breastfeeding history and duration (months).
- Developmental milestone status.
- Other relevant testing/procedures performed and any associated diagnoses.

#### 3.4.6 End of Registry / Premature Discontinuation

All patients should have either the post-partum or the end of registry data collection (Table 3-1) depending on pregnancy outcome. The end of registry data collection will also be done if the patient discontinues from the registry prematurely.

For all infants who did not have the One-Year Follow-up data collection completed the data will be collected at the time of premature discontinuation of the infant's participation.

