## 2 Objective

The overall goal of the Gilenya pregnancy exposure registry is to prospectively collect and evaluate safety data on Gilenya exposure immediately before (up to 8 weeks before last menstrual period (LMP)) and during pregnancy and associated pregnancy outcomes to compare the maternal, fetal, and infant outcomes in the registry to the background frequency from reference populations.

The main (primary) objective is:

• To describe the overall frequency of major and minor congenital malformations associated with exposure to fingolimod during pregnancy.

The other (secondary) objectives are:

- To describe the frequency of specific types of major and minor congenital malformations associated with exposure to fingolimod during pregnancy;
- To characterize the nature of pregnancy and other fetal outcomes associated with exposure to fingolimod during pregnancy such as spontaneous abortions, stillbirths and elective terminations;

• To describe the occurrence of physical developmental delays as well as adverse effects on immune system development in infants around one year of age associated with exposure to fingolimod during pregnancy.

The findings from the Gilenya pregnancy registry will be used to give healthcare providers (HCP) important information for counseling patients treated with fingolimod who become or want to get pregnant.

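### Maternal fingolimod use is not scheduled for collection at the 3-month or one-year follow-up, so in breastfed infants prenatal exposure and possible exposure through milk cannot be separated for the one-year outcomes

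*Protocol*

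**What the plan says.** Protocol section 2 lists, as its last secondary objective, physical developmental delay and "adverse effects on immune system development in infants around one year of age associated with exposure to fingolimod during pregnancy". Section 3.2 defines the exposure: "The exposure of interest is fingolimod exposure during pregnancy or immediately prior to becoming pregnant (up to 8 weeks before LMP".

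Exposure in pregnancy is recorded in detail. The baseline form takes "Fingolimod exposure including dosing and dates of administration including start and end dates of dosing period during various trimesters of pregnancy" (section 3.4.1), and the mid-second-trimester form takes "Updated fingolimod exposure and concomitant medication exposure information" (section 3.4.2). In Table 3-1 the row "Fingolimod dosing and administration" is marked at baseline, mid-second trimester, post-partum, and end of registry or premature discontinuation.

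Section 3.4.6 then states: "All patients should have either the post-partum or the end of registry data collection (Table 3-1) depending on pregnancy outcome". It adds: "The end of registry data collection will also be done if the patient discontinues from the registry prematurely".

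The infant forms are set out in sections 3.4.4 and 3.4.5 and in Table 3-2. None has an item on the mother's fingolimod use. The one-year form does ask for "Breastfeeding history and duration (months", along with immune effects such as serious infections, and developmental milestones.

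**The concern.** The objective links what is seen at one year to exposure before birth. An infant's first year may also include exposure after birth, if the mother resumes treatment while breastfeeding. The plan collects one half of what is needed to identify such infants (whether and for how long the infant was breastfed) but not the other half (whether the mother was taking the drug at the time).

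At stake is the interpretation of hospitalised infections and milestone delays in breastfed infants. If some had exposure through milk, their outcomes would be reported together with those of infants exposed only before birth, and no later analysis could separate them. The breastfeeding item itself also loses much of its value.

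**Working it through.** The plan states no figure on this point, so the check compares the schedules. The only arithmetic is the length of the unrecorded period.

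**Step 1. Scheduled records of maternal fingolimod (Table 3-1).** Baseline; mid-second trimester; post-partum; end of registry or premature discontinuation.

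**Step 2. Which of the last two applies to a live birth followed to completion.** Section 3.4.6 makes the two forms alternatives, depending on pregnancy outcome, and adds the end-of-registry form when a woman discontinues early. A woman with a live birth who does not discontinue therefore has the post-partum form as her last dosing record.

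**Step 3. What the later forms hold.**

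| Form | Maternal fingolimod | Breastfeeding | Immune and developmental outcomes |
|---|---|---|---|
| Post-partum | yes in Table 3-1; absent from the section 3.4.3 list | no | no milestone item; neonatal illness only |
| 3-month (section 3.4.4, Table 3-2) | no | no | no |
| One-year (section 3.4.5, Table 3-2) | no | yes, with duration | yes |

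**Step 4. Length of the gap.** Assume delivery at the EDD.

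Gap = infant age at the one-year form − time of the post-partum form after the EDD

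- Shortest: 10 − 3 = 7 months.
- Longest: 14 − 0 = 14 months.

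**Step 5. Which infants are affected.**

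- Never breastfed: no milk route. One-year outcomes can be described by prenatal exposure as planned.
- Breastfed, mother off treatment: prenatal exposure only.
- Breastfed, mother back on treatment: prenatal exposure plus possible exposure through milk.

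The recorded data do not distinguish the second group from the third once breastfeeding continues past the post-partum form.

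**Step 6. A related inconsistency.** Table 3-1 marks dosing at post-partum, but the item list in section 3.4.3 has no fingolimod update. If the form follows that list, the last scheduled record is the mid-second-trimester form at 21 − 2 = 19 to 21 + 2 = 23 weeks, or the baseline form for women enrolled after week 19. The gap would then start before delivery.

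**The case against.** **Exposure through milk is outside the defined exposure.** Section 3.2 limits it to pregnancy and the eight weeks before the last menstrual period. That is true, but the point does not ask for a new exposure of interest. Postnatal exposure matters here because it can confound the prenatal association that the objective describes.

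**The last column of Table 3-1 may cover completers.** Its window is the end of the patient's participation, section 3.4 counts end of study within the discontinuation period, and section 3.4.8 treats a live-birth report as complete only with one-year data. This reading is arguable, but the either/or sentence in section 3.4.6 speaks against it. A reader might infer that fingolimod use is never recorded after the post-partum form. The documents do not support that: women who discontinue early do get a later dosing record, and the adverse event form can record action taken with fingolimod.

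**Other routes exist.** A hospitalised infection would be a serious adverse event, its relationship to fingolimod must be assessed, and there is a concomitant medication form. The event-based records arise only when an event occurs, so they give no matching information for infants without events. Table 3-1 schedules concomitant medication at the same maternal visits as dosing, and Table 3-2 does not list it.

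**The objective is secondary and descriptive.** This stands and limits the weight of the point. A reader might infer that the one-year outcomes cannot be linked to pregnancy exposure at all, or that the objective cannot be answered. That goes too far: prenatal exposure is recorded with dose and dates, section 5 summarises it by trimester, and never-breastfed infants remain interpretable.

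**Conclusion.** The point holds for breastfed infants of mothers followed to completion. In them, prenatal exposure and possible exposure through milk cannot be separated for the one-year immune and developmental outcomes, because maternal use is unscheduled for about 7 to 14 months. The primary malformation frequency and the never-breastfed infants are unaffected.

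This rests on reading section 3.4.6 as giving completers with a live birth only the post-partum form, and on delivery at the EDD for the length of the gap. The documents give no rate of resumed treatment during breastfeeding, no data on transfer into milk and no background rate of infant infection. The size of any bias cannot be stated, and a reader should not infer a particular inflation of risk.

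This is a cheap improvement to data collection. An analysis plan could not supply it later, since it cannot recover an item that was never collected.

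**What to change.** 1. Add one item to the existing 3-month, one-year and infant premature-discontinuation forms: maternal fingolimod or other disease-modifying therapy since delivery (yes/no), with start and stop dates.
2. Derive the overlap between maternal treatment and breastfeeding. Present the one-year outcomes separately for infants with and without overlap, and use the no-overlap group, which includes the never-breastfed infants, to describe effects associated with exposure during pregnancy.
3. Reconcile Table 3-1 with the section 3.4.3 list on whether fingolimod dosing is collected post-partum, and state in section 3.4.6 whether completers with a live birth also receive the end-of-registry form.

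The cost is one form item on contacts that already take place, and one further split of the one-year tables. For infants already followed, the item can be filled only by recall. Amendment 3 reports 260 women enrolled and section 3 plans for up to about 500, so at most about 500 − 260 = 240 later enrolments could supply it prospectively, plus those enrolled women whose infants have not yet reached the forms. The no-overlap group will be smaller than the full set, so its estimates will be less precise.

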#### 3.4.7 Targeted follow-up

If one or more major or minor malformations are noted, it may be necessary to collect additional information. Signed release forms will be obtained by the enrolling HCP from the mother to acquire maternal and pediatric medical records and permission to contact the appropriate HCP, i.e., obstetrician/gynecologist, and/or pediatrician. Medical records will

allow for case verification. Each potential case will undergo clinical review to confirm status as a congenital anomaly case and to ensure the anomaly (or anomalies) are coded appropriately (i.e., accurately represent the defect or underlying diagnosis). Many terms are used clinically for the same structural or functional defect; therefore, the coding and grouping of anomalies is the key to a meaningful analysis of results. The clinical reviewer will determine what, if any, structural or functional abnormalities are present, if these are minor or major malformations and if there is additional information required to assess the case (e.g., pathology reports, medical records, assessment by neonatologist/pediatrician).

